8.1.4 Secondary Endpoints

- **Duration of cold symptoms** (items 2 to 7) will be assessed by means of the WURSS-K (assessed once daily in the evening).

During treatment period, the WURSS-K will be assessed once daily in the evening, taking in account the symptoms from the morning to the evening.

After D10, the WURSS-K will be assessed once daily until the subject feels not sick for two consecutive days.

For each item, the duration is defined as the number of symptomatic days between D1 and the first day the subject reports not having the symptom for two consecutive days.

To be noticed that the duration may be censored at day 30.

- Number of subjects who develop respiratory complication requiring antibiotic prescription during a 20-day follow-up period. Healsea® Children is expected to reduce acute rhinitis complications.
- Frequency and number of days of use of concomitant treatments that may affect common cold symptoms (antibiotics, antipyretics, mucolytics, decongestants, antitussives, systemic and topical

Version: **2.0**; **08** Sep **2021** Page **30** of **61** Study Number: **LPH-2101**

corticosteroids). By reducing duration of common cold symptoms, Healsea® Children will very likely reduce the use of common rescue medication.

- Number of family members in close contact developing common cold symptoms after the patient all over the study period. The daily use of Healsea® Children started at the onset of common cold symptoms is expected to reduce relative's contamination.
- Safety: Assessment of adverse events/incidents/undesirable expected side effects throughout the study.

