8.1.3 Primary Endpoint

The primary endpoint is the area under the curve (AUC) of the Wisconsin Upper Respiratory Symptom Survey for Kids (WURSS-K) during first 10 days of symptoms. AUC will be calculated applying the trapezoidal rule, with the y-axis, defined by daily WURSS-K scores, and the x-axis, defined as duration of illness, starting with the first symptoms and ending at day 10.

WURSS-K is a 3-dimensional structure questionnaire specifically designed for children 4 to 10 years of age [18] (appendix B). This survey has been demonstrated to be responsible, reliable, and valid for assessing illness specific symptoms and impact on quality of life during an acute infectious rhinitis in paediatric population.

It includes 6 items assessing symptoms (symptoms score: runny nose, stuffy nose, sneezing, sore throat, cough, feeling tired), 7 items assessing functional impairments (quality of life score: think, sleep, breathe, talk, walk/climb stairs/exercise, go to school, play with friends), 1 item assessing global severity. All these items are scored using visual representation of happy and sad faces to assist Likert scale ratings from 0 (absent or no impairment) through 1 (a little bad), 2 (bad) and 3 (very bad). The sum of the 14 items on a 4-point ordinal scale results in a global total score ranging from 0 (low symptoms and low functional impairment) to 42 (high symptoms and high functional impairment). One item assessing global change as compared to the day before is rated from 0 (a lot better) to 4 (a lot worse) is not included in the overall score.

Using an electronic diary, the patient will score the WURSS-K daily in the evening, taking in account the symptoms from the morning to the evening, during D1-D10. After D10, the WURSS-K will be assessed once daily until the subject feels not sick for two consecutive days.

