 incidents/expected undesirable side effects, concomitant medications, and contamination of
 relatives in the e-diary. The legal guardians will access the e-diary website
 (https://me.vieodoc.net) using a smartphone and logging in with a randomly assigned
 username and Pin code. Data recorded in the e-diary will be at the same time uploaded in the
 e-CRF.

D1-D10 (at home):

The patients will be asked to complete the electronic diary daily (WURSS-K assessed once daily in the evening, taking in account the symptoms from the morning to the evening, adverse events/incidents/expected undesirable side effects and concomitant medications, contamination of relatives) and to report Healsea® Children intake if applicable. For the Healsea® Children treated-group, compliance will be indirectly assessed by the question: "do you use the nasal spray as

Version: **2.0**; **08** Sep **2021** Page **35** of **61** Study Number: **LPH-2101**

recommended (1 puff 2 sec in each nostril twice a day)?". If necessary, the parent(s) will help their child in this task.

D5 (Day 5±2, at home): Telephone call 1

The Investigator or his/her delegated designee will call the patient to review patient status and study progress, adverse event/incidents/expected undesirable side effects and concomitant treatments.

Visit 2 (V2) - (Day 10±2): end of treatment

The investigator or his/her delegated designee will:

- Perform a physical and clinical examination,
- Record the common cold symptoms if they persist,
- Validate the adverse events/incidents/expected undesirable side effects and concomitant medications reported in the e-CRF through the e-diary and report any new relevant safety event.

For patients receiving Healsea® children, the treatment will be stopped at D10. The patients for whom common cold symptoms persist, will be instructed to continue to score the WURSS-K until the subject feels not sick for two consecutive days.

D11-D30 (at home):

After D10, the WURSS-K will be assessed once daily until the subject feels not sick for two consecutive days if applicable. The patients will be asked to complete the electronic diary daily (WURSS-K if applicable, adverse events, concomitant medications, and contamination of relatives). If necessary, the parent(s) will help their child in this task.

D20 (Day 20±2, at home): Telephone call 2

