10.2.2. Impact of the treatment chosen on the cold symptoms' duration

Hereinafter, the “recovery date” is the first day of two last days the patient answered to the WURSS-K questionnaire. The patient must have reported a negative answer to the question 1 (“not sick”) and the two last days must be consecutive. Otherwise, there is no “recovery date” for the patient.

For the items 2 to 7 of WURSS-K questionnaire, the duration of the corresponding symptom is defined as the duration between first symptomatic day and last symptomatic day.

Cold symptom's duration (days) = Last symptomatic day – first symptomatic day + 1

For a given symptom, a symptomatic day is a day the patient gave an answer other than negative to the corresponding question (“do not have this”). Missing answers will be imputed by the last observation carried forward (LOCF).

The considered symptomatic days are between D1 and either D30, or the end of the study, or the day before the recovery date, whichever occurs first. Symptomatic days from the recovery date will not be taken into account.

For each of the items 2 to 7 of the WURSS-K questionnaire, the origin date will be the date of the first symptomatic day.

The considered event is the end of the symptom.

For patients who reported a negative answer to the corresponding question on the last day they answered to it, or for patients with a recovery date, the event date will be the last symptomatic day before his/her last day of completion of the questionnaire, or before the recovery date if it exists.

Patients who did not report a negative answer to the corresponding question on the last day they answered to it, and without recovery date, will be censored at D30 or at the end of the study, and the censoring date will be the date of D30 or the reference end date, whichever occurs first.

For patients who never reported the presence of a given symptom (never ticked “a little bad”, “bad” or “very bad”), if they completed the questionnaire at D1, then their origin date will be D1, they will be censored at D1 and their corresponding duration will be zero, else they will have neither origin date nor censoring date and the corresponding duration will be missing.

For each of the items 2 to 7 of the WURSS-K questionnaire, the impact of the treatment chosen on the corresponding cold symptom' duration will be analysed by means of a Cox model. Subjects will be analysed on the FAS.

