12. CHANGES IN THE CONDUCT OF THE STUDY OR PLANNED ANALYSIS

The cold symptoms' duration was defined in the protocol as the number of symptomatic days between D1 and the first day the subject reports not having the symptom for two consecutive days.

Since several patients still reported having symptoms while they reported they did not feel sick anymore at the question 1 during the two last days of completion of the WURSS-K questionnaire, their positive answers to the cold symptoms' items have been considered as non-significant. Consequently, the question 1 has been taken into account instead of the corresponding items to determine the end of the cold symptoms' duration, however only on the condition that the two last days of completion were consecutive.

If the two last days of completion were not consecutive, positive answers to cold symptoms' items are still considered as symptomatic, even if the two last answers to the question 1 are negative. The symptom ends at the last symptomatic day if the patient reported the absence of this symptom after this day. Otherwise, the duration of the symptom is censored at D30 or at the end of the study, whichever occurs first.

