13.3. WURSS-K questionnaire – Daily symptom report

Wisconsin Upper Respiratory Symptom Survey for kids—daily symptom report

Day:	Date:	Time:	ID:
------	-------	-------	-----

Please fill in one circle for each question:

Not sick 	A little sick 	Sick 	Very sick 
How sick do you feel today?			

How bad are your cold symptoms? (Overall, since yesterday)

Do not have this 	A little bad 	Bad 	Very bad 
Runny nose			
Stuffy nose			
Sneezing			
Sore throat (hurts to swallow)			
Cough			
Feeling tired			

Since yesterday, how hard has it been to:

Not at all 	A little hard 	Hard 	Very hard 
Think			
Sleep			
Breathe			
Talk			
Walk, climb stairs, exercise			
Go to school			
Play with friends			

Compared to yesterday, I feel my cold is...

A lot better 	A little better 	The same 	A little worse 	A lot worse 
				

I completed this page: all by myself with some help with a lot of help

Who helped you? _____

Figure 2 – Wisconsin Upper Respiratory Symptom Survey for Kids (WURSS-K) – Daily symptom report

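### After D10 the WURSS-K diary closes on the global 'not sick' answer, so a symptom still present at that stop has no observed end, although its duration is a secondary endpoint

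*Protocol*

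**What the plan says.** **Endpoint.** Protocol 8.1.4 defines duration symptom by symptom: "For each item, the duration is defined as the number of symptomatic days between D1 and the first day the subject reports not having" that symptom on two consecutive days, with possible censoring at day 30. SAP 10.2.2 analyses it with one Cox model per symptom: "For each of the items 2 to 7 of the WURSS-K questionnaire, the impact of the treatment chosen on the corresponding cold symptom' duration".

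**Collection up to D10.** Every child completes the questionnaire: "the patient will score the WURSS-K daily in the evening, taking in account the symptoms from the morning to the evening, during D1-D10" (protocol 8.1.3).

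**Collection after D10.** "After D10, the WURSS-K will be assessed once daily until the subject feels not sick for two consecutive days" (protocol 8.1.4). The deciding question is item 1, "How sick do you feel today", which is separate from items 2 to 7. The same rule stands in the protocol synopsis, flow chart, 8.1.3, 8.1.5 and 8.3.11, and in SAP section 3 with its Figure 1. At Visit 2, persisting symptoms are the reason to go on, but the global answer is again the reason to stop: "The patients for whom common cold symptoms persist, will be instructed to continue to score the WURSS-K until the subject feels not sick" (protocol 8.3.11; the two-day requirement applies here too).

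**Other diary content after D10.** The e-diary itself stays open: "The patients will be asked to complete the electronic diary daily (WURSS-K if applicable, adverse events, concomitant medications, and contamination of relatives") (protocol 8.3.11, D11-D30).

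**Analysis.** SAP section 12 states that "several patients still reported having symptoms while they reported they did not feel sick anymore at the question 1" over their last two days of completion, and treats those positive symptom answers as not meaningful. SAP 10.2.2 sets a recovery date at the first of those two days if they are consecutive, ignores symptomatic days from then on, and counts the symptom as ended.

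**The concern.** The rule that stops data collection does not refer to the quantity being measured. Nothing in either document requires items 2 to 7 to be negative before the questionnaire closes. For a child with a symptom still present at the stop, the two symptom-free days that define the endpoint can no longer be recorded. Visit 3 records symptoms that persist, but gives no date on which a symptom ended.

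Which ends are missing depends on how early the family says 'not sick'. That answer is self-reported in an open-label study in which the family chose the treatment, so it could differ between groups. If it does, the Cox models partly compare the time to feeling well rather than the time to the end of each symptom.

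**Working it through.** **1. The plan's own figure.** The only computed figure is the sample size for the AUC (protocol 7.4, SAP section 4): Cohen's d = 0.4, two-sided 5%, 80% power. n per group = 2 × (1.960 + 0.842)² / 0.4² = 98.1, so 99; power with 100 per group is 80.7%. The stated 100 reproduces. No figure is given for symptom duration.

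**2. Worked diaries under SAP 10.2.2.** Assume continuous cough from D1. Duration = last counted symptomatic day − first symptomatic day + 1, counting days only up to the day before the recovery date.

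| 'Not sick' on | Diary ends | Recovery date | Cough truly lasts to | SAP duration | Status | Days lost |
|---|---|---|---|---|---|---|
| D12, D13 | D13 | D12 | D13 | 11 − 1 + 1 = 11 | event | 2 |
| D12, D13 | D13 | D12 | D15 | 11 | event | 4 |
| D12, D13 | D13 | D12 | D20 | 11 | event | 9 |
| D12, D13 | D13 | D12 | D25 | 11 | event | 14 |
| D9, D10 | D10 | D9 | D14 | 8 − 1 + 1 = 8 | event | 6 |

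The first four children have very different coughs and identical results. In the D13 row the positive days are in the diary but are set aside, and the two symptom-free days that would confirm the end were never collected. In the other rows the end itself is outside the diary.

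**3. Who is affected.** Because D1-D10 is scored by everyone, no diary closes before D10. A symptom whose end is confirmed by two symptom-free days up to D10 is fully observed. The gap concerns only children with a positive item at a stop on or after D10.

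**4. Possible size (assumed inputs).** The documents give neither the share affected nor any group difference in 'not sick'. The illustrations assume 100 per group, gamma-distributed durations (in the main sets, mean last symptomatic day 9 or 11 and mean last sick day 9), correlation between the two from 0 to 0.8, 200 to 400 runs per scenario and no true effect on symptom duration. The hazard ratio is for the end of the symptom in the group that says 'not sick' earlier.

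| Group gap in 'not sick' | Symptom followed to its end | SAP rule | Censored at last diary day | Carried to D30 |
|---|---|---|---|---|
| none | about 1.00 | about 1.00 | about 1.00 | about 1.00 |
| 2 days | about 1.00 | 1.13 to 1.32 | 0.86 to 0.98 | 0.80 to 0.91 |

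With a 1-day gap, one scenario gave 1.12 under the SAP rule and 0.99 with censoring at the last diary day. Under that censoring, the ratio moves further from 1 as the correlation rises. Between 15% and 49% of simulated children still had the symptom at the stop. That share follows from the assumptions and is not a trial figure.

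**The case against.** Several limits are fair, and they stand.

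- **Scope.** A reader might infer that symptom ends go unobserved in general, or that the primary result is affected. Neither follows. Ends confirmed by D10 are recorded, and the AUC uses D1 to D10.
- **Evidence.** A reader might take SAP section 12 as confirming that ends were missed. It confirms discordant answers in several patients, with no count and no split by group. That ends are missing is an inference from the stopping rule, since no WURSS-K is due afterwards.
- **Direction.** A reader might infer that the analysis favours Healsea Children. With no group difference in 'not sick', the simulated ratio stays near 1.00, and no passage shows such a difference.
- **Weight.** Duration is secondary, and SAP 6.3.1 treats all non-primary results as descriptive, with p-values for information only.
- **Analysis-side repair.** It would be too strong to say that censoring cannot help. Lost end dates cannot be recovered, but censoring at the last diary day removes much of the simulated bias when feeling well and symptom end are weakly related. It is less dependable when they are strongly related.
- **Allergy.** All children are sensitised to a perennial allergen, so lingering runny nose, stuffy nose or sneezing may be allergic. This is a real cost of longer follow-up, but not a reason for the present rule: the protocol already defines duration per symptom and foresees censoring at day 30, and neither document gives allergy as the reason for stopping on item 1.

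The burden of longer scoring is a weak objection, because the e-diary is already completed daily to the end of follow-up for other items.

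**Conclusion.** The point holds within those limits. As written, the plan cannot observe the endpoint of protocol 8.1.4 for a child whose symptom is still present when the diary closes on or after D10, and the SAP then records that child as having reached the end of the symptom. This follows from the texts and needs no simulation.

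The size of any bias is unknown. It requires a group difference in when families say 'not sick'. With an assumed 2-day difference, the SAP rule pushes the ratio above 1 in every set of assumptions tried, while censoring at the last diary day or carrying the children to D30 pushes it below 1. The choice of rule can therefore reverse the apparent direction, which is why following each symptom to its end is preferable to choosing among analysis conventions.

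**What to change.** **Collection.** After D10, continue WURSS-K items 1 to 7 daily until items 2 to 7 are all answered as absent on two consecutive days, or until D30. Make the change wherever the rule appears: protocol synopsis, flow chart, 8.1.3 to 8.1.5 and 8.3.11, and SAP section 3 with its flow chart.

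**Diaries already closed.** SAP section 12 describes answers already in hand, so an amendment cannot recover those ends. For these children, report per group how many had each symptom present at the stop. Show each Cox result twice, under the SAP 10.2.2 rule and with those symptoms censored at the last diary day, and state that this censoring may be informative.

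**Cost.** A protocol amendment, a diary setting, and one additional table and analysis. Children with lingering symptoms, some possibly allergic, will have more questionnaire days, capped at D30.

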8.1.5 Methods and timing for assessing, recording and analysing variables

The primary endpoint will be assessed and record into an electronic diary once daily in the evening, considering the symptoms from the morning to the evening, during D1-D10. After D10, the WURSS-K will be assessed once daily until the subject feels not sick for two consecutive days. To be noted that the duration may be censored at day 30. Should the children require some or lot of help to fill in the questionnaire, this will be recorded in the diary as part of the WURSS-K questionnaire.

A specific field will be designed in the electronic diary for adverse event/incidents/expected side effects and concomitant treatments recording, contamination of relative(s) and for report of Healsea® Children intake if applicable.

> 8.1.6 Equipment to be used for assessing the clinical variables and arrangements for the monitoring maintenance and calibration

Not applicable.

8.1.7 Any procedures for the replacement of subjects

Not applicable.

8.1.8 Investigation sites: number, location

The clinical investigation will be undertaken in 15 sites in Poland. All investigators are paediatricians and /or allergist and/or pulmonologists. The investigation does not require specific environment as it is an observational study.

8.1.9 Definition of the completion of the study

This is defined as the date of last patient last visit (LPLV).

8.2 Investigational device and comparator

The investigational device which is Healsea® Children. This is a CE marked Medical Device. Patients/parents will be allowed to use or not the investigational nasal spray. If they choose nasal symptoms to be treated with Healsea® Children, they will start the nasal spray treatment following

Page **31** of **61** Version: 2.0; 08 Sep 2021

their inclusion visit (Visit 1). Healsea® Children will be used on the top of conventional therapies for common cold and administered with the help of an adult, spraying one puff (1-2 sec) twice a day in each nostril for 10 days.

No comparator is used in this study. Patient/parents who prefer not to use Healsea® Children will use conventional therapies for common cold only. **However, use of nasal irrigation will not be authorized for these patients.**

8.3 Subjects

The target population is allergic children with early symptoms of acute infectious rhinitis.

8.3.1 Eligibility criteria

8.3.1.1 Inclusion criteria

Subjects will be enrolled if they meet all of the following criteria:

- 1. Male/Female subjects ≥6 and ≤10- year old
- 2. AsIgE ≥ class 2 (RAST) or positive prick test for at least one perennial allergen
- 3. Acute infectious rhinitis/rhinosinusitis for ≤48h before trial entry
- 4. Patient presenting with fever ≥ 37.5 °C at screening
- Symptoms of headache, muscle ache, chilliness, sore throat, blocked nose, runny nose, cough, sneezing with a total score ≤9 (according to a physician-rated symptom score; scale: 0 → 3 [0: no symptom to 3: severe intensity])
- 6. At least one of these symptoms: sore throat, runny nose or blocked nose (i.e., with a score ≥1)
- 7. Written consent obtained from parent/legal guardians
- 8. Written assent obtained from patient

8.3.1.2 Non-inclusion Criteria

Subjects will not be enrolled if one of the following criteria is present:

- 1. Known hypersensitivity/allergy to any component of the test device
- 2. Medical history that is considered by the investigator as a reason for non-inclusion
- 3. Severe nasal septum deviation or other condition that could cause nasal obstruction such as the presence of nasal polyps
- 4. History of nasal or sinus surgery that in the opinion of the investigator may influence symptom scores
- 5. Antibiotic intake within 2 weeks before screening
- 6. Systemic corticosteroids within 4 weeks before screening
- 7. Antihistamines intake for allergy when treatment was started from less than 4 weeks
- 8. Bacterial lysate intake within 6 months before screening
- 9. Chronic decongestant use

Version: **2.0**; **08** Sep **2021** Page **32** of **61** Study Number: **LPH-2101**

- 10. Recent (within the previous 2 days) intake of a common cold medicine that in the opinion of the investigator may influence symptom score at screening (NSAID, nasal decongestants, cough medicines)
 - 8.3.2 Criteria and procedures for subject withdrawal or lost to follow-up

8.3.2.1 Withdrawal Criteria and procedures

The reasons for a subject's premature withdrawal from the study may be the following:

- A parent can withdraw his/her consent and/or a subject can withdraw his/her assent from the study for any reason at any time, but he/she must inform the investigator. In all cases, whenever possible, the investigator should attempt to contact the patient as soon as possible for a final assessment in order to:
 - Obtain the reason(s) for withdrawal and report it/them in the Case Report Form,
 - Evaluate the patient's clinical condition,
 - o If necessary, take appropriate therapeutic measures: management of an adverse effect or concomitant disease, prescription of another treatment.

An investigator may discontinue or withdraw a participant from the study for the following reasons:

- If any clinical adverse event (AE), laboratory abnormality, or other medical condition or situation occurs such that continued participation in the study would not be in the best interest of the participant.
- If the participant meets an exclusion criterion (either newly developed or not previously recognized) that precludes further study participation. In the context of COVID-19 pandemic, the diagnosis of COVID-19 during the study will justify the withdrawal of the patient from the study.

A premature end of study visit will be scheduled. Available data will be retained for the safety/efficacy analysis.

